3.10 Height, Weight and BMI

Height will be measured at Screening only. Body weight will be measured at scheduled visits as specified in Section 2. The subject will wear lightweight clothing and no shoes during weighing. BMI calculations will be done at the Screening Visit to assess Inclusion criterion #3 of the protocol.

COVID-19 Pandemic-Related Acceptable Protocol Modifications

In the event this may not be performed due to study modifications related to the COVID-19 pandemic, body weight will be measured at the next earliest feasible visit.

3.11 Vital Signs

Vital sign determinations of systolic and diastolic blood pressure, pulse rate, and body temperature will be obtained at visits as specified in Section 2. Blood pressure and pulse rate should be measured and documented after the subject has been sitting for at least 3 minutes both before infusion and at the end of infusion. Repeat vital sign determinations should be taken from the same extremity as initial determination.

Following infusion, if the blood pressure is elevated above 160 mmHg systolic (and 20 mmHg over preinfusion value) OR 105 diastolic (and 15 mmHg over pre-infusion value), then the heart rate and blood pressure measurement should be repeated. If the blood pressure remains elevated above these thresholds, the investigator should repeat the measurement after one hour. If the elevation persists, the investigator should further assess and manage the subject according to standard of care. If the subject is symptomatic (e.g., chest pain, headache, neurologic symptoms, visual disturbances, perturbations in other vital signs) or has cardiovascular comorbidities of concern, an ECG, additional cardiac monitoring, and treatment with anti-hypertensive agents at the site or emergency care setting should be considered. If a subject leaves the site with a blood pressure exceeding the above thresholds, a follow-up phone call from the site to the subject approximately 12 hours later is recommended and the subject should return for an unscheduled follow-up visit approximately 48 hours later with blood pressure and heart rate documented by the site. While not anticipated, sustained blood pressure elevations beyond the thresholds described above should be assessed and managed by the investigator or the subject's physician.

COVID-19 Pandemic-Related Acceptable Protocol Modifications

In the event this may not be performed due to study modifications related to the COVID-19 pandemic, vital signs will be measured at the next earliest feasible visit.

3.12 Physical Examination

A complete physical examination will be performed at the designated study visits as specified in Section 2. Height and body weight will be measured at Screening in order to calculate body mass index (BMI). Body weight will also be measured at Week 0 – Baseline and at each treatment visit or upon subject discontinuation. The subject will wear lightweight clothing and not wear shoes when taking height and weight at Screening and when taking weight at subsequent visits. The physical examination performed on Week 0 – Baseline will serve as the baseline physical examination for the entire study. Any significant physical examination findings after the first dose will be recorded as AEs. All findings, whether related to an AE or part of each subject's medical history, will be captured on the appropriate eCRF page.

At any time, a symptom-directed physical examination can be performed as deemed necessary by the investigator.

COVID-19 Pandemic-Related Acceptable Protocol Modifications

In the event this may not be performed due to study modifications related to the COVID-19 pandemic, physical examination will be performed at the next earliest feasible visit.

3.13 Neurological Examination

A neurological examination will be performed at the designated study visits as specified in Section 2. A symptom-directed neurological examination will be performed when necessary. Portions of the neurologic exam that are required to complete the EDSS will be performed at visits where the EDSS is calculated. The neurological examination performed at Week 0 - Baseline will serve as the Baseline for clinical assessment. Symptoms identified during screening will not be recorded as adverse events, however, new symptoms or current symptoms that change in severity or frequency after the first infusion of study drug will be recorded as adverse events.

The neurological examination will assess:

- Mental status assessment of orientation, speech, and memory.
- Cranial nerves assessment of cranial nerves II XII.
- Motor system –assessment of tone and strength, including assessment for tremor.
- Sensory system assessment of light touch, temperature and distal proprioception
- Reflexes assessment of deep tendon reflexes and plantar responses (Babinski sign)
- Coordination assessment of upper and lower extremities
- Gait gait, including tandem

COVID-19 Pandemic-Related Acceptable Protocol Modifications

In the event this may not be performed due to study modifications related to the COVID-19 pandemic, neurological examination will be performed at the next earliest feasible visit.

3.14 Actigraphy

A wearable sensor will be used (when allowed per local regulatory guidelines) to enable data capture on actigraphy (activity, rest cycles) and daily step count. If regulatory approval in a participating country has not been received by the manufacturer, actigraphy data monitoring will not be done in that country. The actigraphy assessment will use BioStamp nPoint, which is a wireless remote monitoring platform intended for use by healthcare professionals and researchers for the continuous collection of physiological data in healthcare and home settings. BioStamp nPoint is designed to capture objective, real-world data from study subjects participating in clinical or academic studies and may be used wherever collection of relevant data is needed. BioStamp nPoint centers on body-worn BioStamp Sensors that can be worn for up to 24 hours at a time.

When BioStamp nPoint is used in the home or outside of the clinic ("Remote") setting, study subjects interact with the system through a Mobile Phone Application called the "Link App." The recharging and data transmission hub ("Link Hub") is used to recharge the sensors and synchronize data from the Sensors. The system is also capable of surface electromyography (sEMG) and monitoring limb and body movements during daily living and sleep. Training will be provided to site staff with instructions for subject use. Refer to Section 2 for the required administration times.

COVID-19 Pandemic-Related Acceptable Protocol Modifications

In the event this may not be performed due to study modifications related to the COVID-19 pandemic, actigraphy data will be captured at the next earliest feasible visit.

3.15 Assignment of Subject Numbers and Use of Interactive Response Technology (IRT)

Contact information and user guidelines for IRT use will be provided to each site.

At the Screening visit, all subjects will be assigned a unique subject number through the use of the IRT system.

IRT has adopted the following numbering convention:

- 1st digit Lead 1
- 2nd, 3rd, and 4th digits 3 digit site # 100 199 (sequence for Canada begins with 200)
- 5th and 6th digits sequential subject number

For subjects who do not meet the study selection criteria, the site personnel must update the IRT system and identify the subject as a screen failure.

Subjects who are enrolled will retain their subject number assigned at the Screening visit throughout the study.

Upon receipt of study drug, the site unblinded pharmacist will acknowledge receipt in the IRT system.

Eligible subjects will be randomized in a 1:1:1 ratio to elezanumab **sector** or elezanumab **sector** or placebo through the IRT. The IRT system will assign the kit number(s) to be used at each visit for dose preparation for a given subject in accordance with the subject's assigned randomized treatment.

3.16 Clinical Laboratory Tests

Blood samples will be collected before study drug administration. The baseline laboratory test results for clinical assessment for a particular test will be defined as the last measurement before the initial dose of study drug. Laboratory re-tests during Screening are allowed if, in the investigator's opinion, the initial result potentially resulted from test variability or was a non-clinically significant perturbation that has since resolved.

Clinical Laboratory Tests		
Hematology	Clinical Chemistry	Other Tests
Hematocrit Hemoglobin Red blood cell (RBC) count White blood cell (WBC) count Neutrophils Bands Lymphocytes Monocytes Basophils Eosinophils Platelet count (estimate not acceptable) Activated partial thromboplastin	Blood urea nitrogen (BUN) Creatinine Creatine phosphokinase (CPK) Total bilirubin Albumin Alanine transaminase (SGPT/ALT) Aspartate transaminase (SGOT/AST) Alkaline phosphatase Sodium Potassium Calcium Inorganic phosphorus Uric acid	Human immunodeficiency virus (HIV) Hepatitis B surface antigen (HBsAg) Hepatitis C virus (HCV) Serum pregnancy test Serum PK Serum PD Serum ADA DNA/RNA pharmacogenetics
Urinalysis	Total protein Glucose	
Specific gravity Ketones pH Leukocytes Nitrite Protein Blood Glucose Urine pregnancy test Microscopic exam	Triglycerides Bicarbonate/CO ₂ Chloride	

Covance, a certified central laboratory, will be utilized to process and provide results for the clinical laboratory tests. Laboratory reference ranges will be obtained before the initiation of the study.

Instructions regarding the collection, processing, and shipping of these samples will be provided by the central laboratory and sent to the following certified laboratory address:

Covance Central Laboratories Services, Inc. [name]

All laboratory abnormalities that occur during the study must be evaluated by the investigator to determine if they indicate a new disease process, an exacerbation or worsening of an existing condition, or require further action to be taken, and therefore, may need to be reported as AEs. Accordingly, for any values outside of the reference range, the investigator will indicate on the report if the result is clinically significant (CS) or not clinically significant (NCS). If a laboratory abnormality meets criteria for a potentially clinically significant (PCS) laboratory value, as defined in Appendix B, the investigator must either report an associated AE or document in source the reason(s) the finding was not considered an AE.

Any laboratory value that remains abnormal at Completion/Early Discontinuation and was judged to be CS, will be followed according to accepted medical standards until resolution of the abnormality.

Pregnancy Tests (Serum and Urine)

A pregnant or breastfeeding female will not be eligible for participation or continuation in this study.

Pregnancy testing should not be performed for postmenopausal females. Determination of postmenopausal status is made during screening based on the subject's history.

A quantitative serum pregnancy test will be performed at Screening and a urine pregnancy test will be performed at the Week 0 – Baseline visit for all female of childbearing potential subjects.

The serum pregnancy test will be sent to and performed by the central laboratory. If the serum pregnancy test is positive, the subject is considered a screen failure. If the serum pregnancy test is borderline, it should be repeated \geq 3 days later to determine subject eligibility.

If the repeat serum pregnancy test is:

- Positive, the subject is considered a screen failure;
- Negative, the subject can be enrolled into the trial;
- Borderline > 3 days later, this will be considered documentation of continued lack of a positive result and the subject can be enrolled into the study (unless prohibited per local requirements) in the absence of clinical suspicion of pregnancy and other pathological causes of borderline results.

Additional urine pregnancy tests will be performed at visits indicated in the Activity Schedule. The results of the monthly at home pregnancy tests must be communicated to the site. More frequent pregnancy tests can be performed throughout the study at the investigator's discretion or if required per local/country requirements.

- If the baseline urine pregnancy test is negative, then dosing with study drug may begin.
- If the baseline or post-baseline urine pregnancy test is positive, dosing with study drug must be withheld and a serum pregnancy test is required (as stated above).

Urinalysis

Urinalysis will be completed by the central laboratory at all visits that state "Central Laboratory Tests" per Appendix D, Activity Schedule, in the protocol. Specified abnormal macroscopic urinalyses defined as leukocytes, nitrite, protein, ketones, or blood greater than negative, or glucose greater than normal will be followed up with a microscopic analysis at the central laboratory.

COVID-19 Pandemic-Related Acceptable Protocol Modifications

If travel restrictions or other changes in local regulations in light of the COVID-19 pandemic prevent the subject from having blood drawn for laboratory testing at the study site, if possible, arrange for subjects to have laboratory work done at a local laboratory, hospital, or other facility. Local laboratory results should be obtained along with reference ranges and kept within the subjects' source documentation. Local laboratory results should be reviewed by the investigator as soon as possible.

3.17 Magnetic Resonance Imaging (MRI)

Preparation for the MRI exam before the subject's arrival is critical in order to ensure that all scans can be acquired within the allotted time frame and for accommodation of any unforeseen delays. MRI scanner must have a magnetic field strength of 1.5 Tesla or 3 Tesla. 3 Tesla scanners are preferred so these should be used whenever both field strengths are available. The total scan time, not including subject position, is estimated to take approximately 50 minutes depending on the type of scanner. The imaging facility is responsible for the MRI safety of subjects who are scanned at the imaging facilities, all procedures and guidelines for safety consideration should be followed. A MRI safety questionnaire, if part of the standard of care at the investigative site, should be administered to ensure that the subject does not have any of the MRI contraindications.

For imaging session involving gadolinium contrast agent administration, an intravenous catheter for gadolinium contrast agent infusion will be inserted according to standard clinical practice to all subjects. The subjects will be positioned supine on MRI bed and their head will be positioned within a head coil with appropriate foam padding to minimize movement during the scan and to standardize the orientation of the head. The subjects will then be positioned within the MRI scanner for imaging. Scans that are of poor quality (e.g., due to head motion during the scan, inadequate coverage of the brain, improper positioning of the head, use of incorrect scan or geometry parameters, or noisy image) as determined by the MRI technologist, reviewing radiologist or sponsor, will be repeated at earliest time possible and within 15 days of the protocol-required time point.

Following completion of the MRI scan, subjects will be transported from the imaging center back to the study site, if applicable. Sedation is not recommended but is allowed. Subjects who might need sedation should discuss this with the principal investigator before the imaging procedure. Sites are to record any sedation medication on the Concomitant Medications eCRF. The MRI technician is responsible for performing brain MRI scans at all protocol-required time points.

During the course of the study, MRI scans will be performed at three time points: at Screening (Baseline MRI), Week 24 and Week 52/Early Discontinuation. The screening MRI will be evaluated by the local radiologist and the radiologist's report reviewed by the investigator before Dose 1 at Week 0-Baseline visit to determine subject's eligibility. For the subjects enrolled in the study, the Screening MRI will

serve as the Baseline MRI for assessment of MRI outcome measures. The time window for MRI is \pm 7 days. MRI scans from all protocol-required time points will be evaluated by a local radiologist, and the local radiologist's reports will be reviewed by the site investigator for disease activity. Sites should use the same local radiologist to evaluate all the MRI collected through the entire duration of the study to the extent possible.

The MRI scans will include all or a subset of the following parameters:

- 3D T1 weighted
- T2 FLAIR
- MTR
- PD/T2
- T1 post Gadolinium
- DTI
- Spine STIR

For each study site, the MRI scanner, associated equipment and imaging parameters may not be changed during the length of the study without prior sponsor approval.

COVID-19 Pandemic-Related Acceptable Protocol Modifications

MRI assessments may be collected up to 12 weeks after the projected visit for the missed time points at Weeks 24 and 52 with the sponsor's consent due to reasons related to the COVID-19 pandemic. However, all MRI assessments projected to be obtained on or before mid-November 2020 must be completed by the end of November 2020.

To accommodate scheduling of the vast volume of projected Week 52 MRIs in December 2020, at the discretion of the sponsor, sites may schedule Week 52 MRIs up to -28 days of their projected Week 52 visit.

3.18 Dispense Study Drug

The unblinded pharmacist or qualified designee, under direct supervision of the unblinded pharmacist, will prepare study drug for IV administration. The unblinded pharmacist or qualified designee will dispense the blinded study solution to the clinic staff for IV administration to subjects beginning at the Week 0 – Baseline visit after all other Week 0 – Baseline procedures are completed.

Each site will be responsible for maintaining drug accountability records including product description, manufacturer, and lot numbers for all non-investigational products dispensed by the site.

Further information about study drug is in protocol Section 5.7.

COVID-19 Pandemic-Related Acceptable Protocol Modifications

In the event that study drug is not able to be administered due to study modifications related to the COVID-19 pandemic, bring the subject in as soon as possible for their missed infusion. Utilize the

allowable visit windows to shift the subject into their predicted visit schedule. There needs to be a minimum of 14 days between infusions.

3.19 Subject Withdrawal from Study

All attempts must be made to determine the primary reason for discontinuation of study drug or study participation. The information will be recorded on the appropriate eCRF page. Following discontinuation of study drug, the subject will be treated in accordance with the investigator's best clinical judgment.

Each subject has the right to withdraw from the study at any time. In addition, the investigator may discontinue a subject from the study at any time if the investigator considers it necessary for any reason, including the occurrence of an adverse event or noncompliance with the protocol.

Severe allergic reactions or other adverse events that require the immediate interruption of elezanumab treatment will be taken into consideration by the AbbVie TA MD for permanent discontinuation from further treatment and initiation of appropriate medical therapy and follow-up.

Any treatment-emergent, clinically significant, symptomatic neurological abnormalities and treatmentemergent MRI findings will be reported to the AbbVie TA MD and subjects will be considered for discontinuation from treatment if clinically indicated.

Subjects at risk of suicide as indicated by answering yes to question 4 or 5 on the C-SSRS and/or determined by the investigator to be at risk of suicide, should be promptly referred for appropriate follow-up care. Subjects determined to be at ongoing risk of suicide should be discontinued from study participation.

If a subject has a positive drug screen, including for amphetamines, cannabis, opioids, and benzodiazepines, the subject will be discontinued from study participation unless allowed to be taken in accordance with a physician's prescription.

If for any reason the subject becomes unable to continue treatment with elezanumab (other than missed doses due to COVID-19 pandemic modification), undergo protocol required procedures, or otherwise continue to participate in the study, discontinuation should be discussed with the AbbVie TA MD.

In the event that a subject withdraws or undergoes early discontinuation from the study, the primary reason for discontinuation and any other reason(s) for the discontinuation from the study will be recorded and the Early Discontinuation assessment will be performed as per Section 2 and protocol Appendix D, Activity Schedule. The Early Discontinuation visit should be performed as soon as possible, preferably within 2 weeks, after discontinuation from the study. Additional blood samples for drug measurement may be collected at the time of discontinuation from subjects who are discontinued due to adverse events; the clock time, time in relation to dose and date the sample was taken will be recorded.

If a subject is discontinued from the study with an ongoing adverse event or an unresolved laboratory result that is significantly outside of the reference range, the investigator will attempt to provide followup until a satisfactory clinical resolution of the laboratory result or adverse event is achieved.

In the event that a positive result is obtained on a pregnancy test for a subject or a subject reports becoming pregnant during the study, the administration of study drug to that subject must be discontinued immediately. The investigator must report a pregnancy within 1 working day of the site being aware to one of the AbbVie representatives listed in Section 1.

3.20 Unscheduled Visits

An unscheduled visit should be performed when the subject comes in for a medical visit for evaluation and assessment. During Unscheduled Visits, blood and urine samples may be obtained for the laboratory tests listed in Section 3, or for other tests, at the investigator's discretion.

Visits to only retest a lab will not be considered an Unscheduled Visit.

4 SAFETY MANUAL

4.1 Methods and Timing of Safety Assessment

All adverse events reported from the time of study drug administration until 39 weeks (5 half-lives) following discontinuation of study drug administration have elapsed will be collected, whether elicited or spontaneously reported by the subjects. In addition, serious adverse events and protocol-related nonserious adverse events will be collected from the time the subject signed the study-specific informed consent.

Adverse event information will be collected as shown below.

Relapse Assessments

Any appropriate new neurological abnormality which is consistent with new or worsening neurological symptoms reported by the subject, which may or may not be accompanied by new findings in other systems, may qualify as a relapse. This also includes focal neurological dysfunction that may not be accompanied by objective neurological findings (e.g., change in sensory perception with myelitis or change in visual acuity/color perception with optic neuritis). Qualification as a relapse requires meeting the following criteria:

- A new or worsening neurological symptom or set of symptoms
- Occurring in the absence of fever
- Lasting for \geq 24 hours
- Preceded by at least 30 days of clinical stability or improvement

Documentation and follow-up of each suspected relapse will be conducted throughout the study period with scheduled and unscheduled neurological assessments. Subjects will be instructed to inform the study site within 48 hours of the onset of relapse symptoms. When a subject calls to report a suspected relapse, the study site personnel will discuss the symptoms with the subject and determine whether a neurological assessment is indicated.

If so, an unscheduled visit to the study site should be arranged for the subject as quickly as possible, preferably within no more than seven (7) days of onset of relapse symptoms. During each suspected relapse, the blinded physician investigator will determine the nature of the relapse and conduct a full neurological assessment before reviewing previous neurological assessments. After completing the neurological assessment and the source document, the blinded physician investigator may then discuss the new neurological symptoms with the subject. The study nurse/coordinator may then provide the previous neurological examination document to the blinded physician investigator to help determine if a relapse has occurred and to assess its severity (based on revision of the current and previous neurological examinations and discussion with the subject about activities of daily living).

The blinded physician investigator will determine whether a relapse has occurred or not, and whether it will count as a qualifying relapse as defined above.

Subjects who experience a suspected MS relapse may be treated with intravenous (IV) methylprednisolone for 1 to 5 consecutive days, or another corticosteroid or corticosteroid precursor regimen so long as consistent with good neurological practice. Subjects not currently receiving maintenance immunomodulators, must be counseled that immunomodulators have been demonstrated to significantly decrease relapse frequency. Site staff are to ensure eCRFs are completed capturing rescue concomitant medication and documenting relapse on the AE eCRF.

They will subsequently be handled as follows:

- Subjects may elect to receive no IV methylprednisolone or other corticosteroids/corticosteroid
 precursor as described above and not initiate maintenance immunosuppressive therapy. As
 stated above, they must be counseled that approved MS immunomodulators have been
 demonstrated to significantly decrease flare frequency in MS subjects. They will continue to
 receive elezanumab or placebo.
- Subjects may receive IV methylprednisolone for 1 to 5 consecutive days (or other corticosteroids/corticosteroid precursor according to good neurological practice) but elect not to begin maintenance immunosuppressive therapy. They must be counseled that approved MS immunomodulators have been demonstrated to significantly decrease flare frequency in MS subjects. They will continue to receive elezanumab or placebo.
- Subjects may begin receiving an immunomodulator that is recommended by their treating physician and is considered to provide the best balance of benefit versus risk. If the prescribed

medication is one that is allowed in the protocol's Inclusion Criterion #10, the subject can continue in the trial. If another immunomodulator is prescribed, they will not receive further infusions and should be discontinued from the study.

In the event of a clinical MS relapse, a supplemental AE eCRF form should be completed (See Appendix C, Relapse Questionnaire).

Adverse Events of Special Interest (AESI)

Infusion Reactions

The investigator or qualified designee will evaluate the infusion site area from Week 0 – Baseline through the end of the study. Any observation of infusion site reaction after the start of infusion must be recorded as an adverse event (AE).

Further information on monitoring of elezanumab infusion reactions is presented in Appendix D.

Collection of Data Regarding Known Complications of the Disease Under Study

Natural progression of MS (including new or worsening neurological symptoms and signs) is expected in the subjects. Disease progression will be assessed at pre-determined intervals throughout the treatment period by standardized criteria (such as the EDSS+, MSIS-29 version 2, MFIS, MSIOA) and recorded within the electronic Clinical Outcome Assessments (eCOA) for risk/benefit determinations. Therefore, "disease progression" or other similar verbatim terms related to disease status SHOULD NOT be recorded on the AE case report form (CRF) pages. Falls will not be recorded as AEs unless they lead to other injury or represent a change in frequency or character from pre-randomization falls.

Similarly, the slow progression of pre-existing disease-related signs and symptoms clearly associated with the disease during the treatment period will not be reported as AEs unless these signs and symptoms are judged by the investigator to have become unusually severe or accelerated, or if the investigator suspects the deterioration of disease-related signs and symptoms to be potentially related to the investigational drug. If there is any uncertainty about the worsening of an AE being due solely to the disease under the treatment protocol, it should be reported as an AE or SAE as appropriate.

Discontinuation from this treatment protocol because of progression or deterioration of the disease should be recorded on the Study Completion eCRF page as discontinuation due to "disease progression" and NOT as discontinuation due to an AE.

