10.2.2 Adverse Event Overview

The number and percentage of subjects experiencing one or more TEAEs in the following adverse event categories will be summarized for each treatment group, combined elezanumab group and all subjects overall:

- Any TEAE
- Any TEAE that are considered related to study treatment
- Any severe TEAE
- Any serious TEAE
- Any TEAE leading to discontinuation of study treatment
- Any AE of Special Interest
- Any TEAE leading to death
- Death

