10.2.8 Listings of Adverse Events

The following additional summaries of adverse events will be prepared.

- Listing of all deaths for all subjects screened
- Listing of all serious TEAEs
- Listing of all pre-treatment serious AEs for all subjects screened
- Listing of all TEAEs that led to discontinuation of study treatment

- Listing of subjects with treatment-emergent adverse event of special interest

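### Operations Manual 4.1 makes accelerated or possibly drug-related worsening a reportable AE, then bars a stop for disease deterioration from being coded as due to an AE, and the SAP does not say which field feeds its TEAE-discontinuation outputs

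*Protocol*

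**What the plan says.** Operations Manual 4.1, under the heading on known complications of the disease under study, sets two rules.

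**What is an AE.** Slow progression of existing MS signs and symptoms is not reported, "unless these signs and symptoms are judged by the investigator to have become unusually severe or accelerated". Suspected causality is a further exception: the worsening also becomes reportable "if the investigator suspects the deterioration of disease-related signs and symptoms to be potentially related to the investigational drug". If it is uncertain whether a worsening is due to the disease alone, "it should be reported as an AE or SAE as appropriate".

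**How a stop is coded.** "Discontinuation from this treatment protocol because of progression or deterioration of the disease should be recorded on the Study Completion eCRF page", with disease progression as the reason, "and NOT as discontinuation due to an AE". The exceptions in the first rule are not repeated here.

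The SAP then reports stopping in two places:

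- Section 6.0 tabulates the reasons for study drug discontinuation and study discontinuation by treatment group, both all reasons and the primary reason.
- Section 10.2.2 has the overview line "Any TEAE leading to discontinuation of study treatment". Section 10.2.4 repeats it by system organ class and preferred term, and 10.2.8 adds a "Listing of all TEAEs that led to discontinuation of study treatment".

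Neither document says which eCRF field marks a TEAE as having led to discontinuation.

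**The concern.** The two rules overlap. A worsening that the investigator has reported as an AE, because it was accelerated or possibly related to study drug, is still a deterioration of the disease in the ordinary sense of the words. If it ends treatment, the first rule calls it an AE and the second tells the site not to record the stop as due to an AE.

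What is at stake is the link between the event and the stop, which is what a TEAE-leading-to-discontinuation table exists to show. Elezanumab acts on the nervous system and the trial population has MS. Neurological worsening that ends treatment is therefore a harm the tolerability tables should be able to display separately from expected progression.

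**Working it through.** The plan gives no figure on this point to reproduce, so the check is mainly a comparison of the texts.

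**Step 1: apply both rules of Operations Manual 4.1 to each kind of worsening that leads to a stop.**

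| Worsening | Reportable as AE? | Reason for the stop, read literally | Consistent? |
|---|---|---|---|
| Slow, expected progression | No | Disease progression | Yes |
| Unusually severe or accelerated | Yes | Disease progression, not AE | No |
| Suspected to be drug-related | Yes | Disease progression, not AE | No |
| Cause uncertain | Yes, AE or SAE | Disease progression, not AE | No |

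The coding rule fits only the first row.

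**Step 2: look for a provision that resolves it.** Operations Manual 3.19 has the site record a primary reason and any other reasons for discontinuation. That would allow an AE as a second reason, but the explicit prohibition in 4.1 tells the site not to give it. No other section lifts the prohibition.

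**Step 3: follow such a subject into the SAP outputs under each possible source of the flag.**

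- *Flag taken from the AE page.* The TEAE is counted in 10.2.2, 10.2.4 and 10.2.8. The disposition table in 6.0 shows disease progression for the same subject. The two tables then differ, and no rule reconciles them.
- *Flag taken from the Study Completion reason.* The TEAE is not counted as leading to discontinuation in 10.2.2, 10.2.4 or 10.2.8. It still appears by system organ class and preferred term (10.2.3, 10.2.4), by maximum severity (10.2.5) and by maximum relationship (10.2.6). If serious, it also appears in the serious-TEAE table and listing (10.2.4, 10.2.8).

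Under either source, the disposition table alone does not separate AE-qualifying worsening from expected progression. The SAP plans no listing or cross-tabulation that joins the two.

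**Step 4: scale.** The input is 55 subjects per arm (Protocol 7.3, SAP 4.4).

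- One subject in one arm: 1/55 = 0.018, or 1.8 percentage points.
- Assumed range of 1 to 5 affected subjects in one arm: 1/55 = 1.8 to 5/55 = 9.1 percentage points.
- One subject in the combined elezanumab column (2 × 55 = 110): 1/110 = 0.9 percentage points.

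The range of 1 to 5 is an assumption. The 10% dropout in SAP 4.4 is an all-cause planning value and gives no rate for stops of this kind.

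**The case against.** The strongest reply is that the coding rule governs a single field, the reason on the Study Completion page. It does not remove the AE or say how the AE page records what was done with study drug. If the SAP flag comes from the AE page, the TEAE-discontinuation outputs lose nothing. This stands. A reader might infer that these cases are certainly missing from those outputs, but the documents do not show it, because the source field is not stated.

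A second reply is that worsening suspected to be drug-related is arguably not a stop because of the disease, so the coding rule would not reach it. That reading is possible, but it depends on the site adopting it against an unqualified prohibition. It helps least for accelerated worsening that is still attributed to MS.

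A third reply is that the event remains visible. It is in the TEAE tables by preferred term and relationship, and an imbalance in disease-progression stops would show by arm in the disposition table. Operations Manual 3.19 also sends treatment-emergent, clinically significant, symptomatic neurological abnormalities to the sponsor's medical director. This stands too, so it would be wrong to infer that such worsening cannot be told apart from ordinary progression anywhere in the report.

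A reader might also extend the point to relapses. The documents do not support that. Relapses have their own AE documentation and their own summary (SAP 10.7), and the stated trigger for discontinuation after a relapse is the prescription of a non-allowed immunomodulator, not deterioration.

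**Conclusion.** The contradiction in Operations Manual 4.1 is established from the text: worsening can be a reportable AE while the stop it causes may not be coded as due to an AE. The direct consequence is that, where sites follow the rule literally, such stops appear as disease progression in the SAP 6.0 tables.

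Loss from the TEAE-discontinuation outputs is conditional. It follows only if the flag is taken from the Study Completion page. The AE itself is not lost. Each affected subject is worth 1.8 percentage points in an arm of 55; the number affected is unknown. Safety is summarised without hypothesis tests (SAP 10.1), so no inference is at risk, only the accuracy of a descriptive table in which small counts are read closely. The documents do not rank these events above other harms, and the point does not need them to. It should be corrected because a stated rule produces a wrong coding result.

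**What to change.** 1. **Operations Manual 4.1.** Reconcile the two rules by limiting the disease-progression coding to worsening that is not reportable as an AE under the same section. If the worsening was reported as an AE or SAE, record the discontinuation as due to that event. Say also whether the rule concerns stopping study drug, leaving the study, or both, since its wording leaves this open.
2. **SAP 10.2.2, 10.2.4 and 10.2.8.** State that the flag is derived from the AE record. Count a TEAE that led to stopping even when disease progression is the Study Completion reason.
3. **SAP 10.2.8.** Add a listing of disease-progression discontinuations, by arm, with any concurrent neurological TEAE and its severity and relationship.

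Protocol Appendix E states that all subjects had completed 52 weeks of therapy by January 2021. The first change would therefore not alter how past stops were coded without retrospective review. The SAP changes can still act, because Protocol 4.1 places the final safety analyses after the Follow-Up Period.

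The cost is a sentence in the manual, a sentence in the SAP and one short listing. The count of AE discontinuations may rise slightly. The second change assumes that the AE page records whether study drug was stopped; the eCRF is not among the documents. If it does not, the cases found through the listing would need individual review. No dose, schedule or stopping criterion changes.
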